Longitudinal Study of Dental Implant Therapy in HIV Positive Patients

Study Protocol & Statistical Analysis Plan

NCT01211288

August 30, 2019

[name], DMD, Principal Investigator
University of Alabama at Birmingham
[name]

APPENDIX 1

Protocol

D-2007-51

PROTOCOL SYNOPSIS

Title

Longitudinal Study of Dental Implant Therapy in HIV Positive Patients

Investigator (*Insert here the name, mailing address, email address, and phone number of the Co-ordinating Investigator (for multi-centre studies) or the Principal Investigator (for single-centre studies)*)

A. Principle Investigator:

[name], MS, DMD, FAGD, FACD
Prosthodontist, Associate Professor, UAB Comprehensive Dentistry Department
[name]
[name]
[contact]
[contact]

B. Co- Investigators:

1. [name], DMD
General Dentist, Assistant professor, Director 1917 HIV/AIDS Dental Clinic, UAB Comprehensive Dentistry Department
2. [name], DMD, FAGD, MAGD
Assistant clinic professor, UAB Comprehensive Dentistry Department
Private Practice General Dentistry, Wedowee AL.
3. [name] - [name], MS, DMD
Prosthodontist, Professor and Chair, UAB Comprehensive Dentistry Department
4. [name], DMD, PHD
Prosthodontist, Associate Professor, UAB Comprehensive Dentistry Department
5. [name], DMD
Radiologist, Associate Professor, Director of Clinical Operations and Dental Radiology, UAB Diagnostic Science Department
6. [name], MS
Oral and Maxillofacial Pathologist, Assistant Professor, UAB Anatomic Pathology Department

<>>

Study centre(s) and number of subjects planned (*Insert here the address where the study will be conducted, number of patients planned and if applicable distribution of patients per site*)

1. UAB School of Dentistry
Department of Comprehensive Dentistry
[name]
[name]

Total 40 patients will be treated in the 2nd floor main clinic
 20 HIV (+) patients will be selected from the 1917 Dental Clinic and 20 patients will be selected from UAB School of Dentistry patients.

2. Cone Beam CT scanned at UAB School of Dentistry Periodontal research clinic

<>>

Study period

<<Month and year>>

<<Month and year>>

Estimated Start date and End date

January 2010

December 2014

Date of first data available for presentation

December 2011

Objectives (Insert objectives)

1. To study the short term and long term osseous integration of implant supported restorations on immunocompromised (HIV positive) patients.
2. Radiographic examination of implant osseous integration using Cone Beam CT and traditional vertical bitewing radiographs.
3. Histologic examination of bone biopsies from each implant surgical site, at the time of initial placement, and from failing implant sites, including histologic examination of the implant-bone interface.

Study design (Insert a one-sentence summary of study design features)

Provide HIV (+) patients with implant supported restorations, using HIV (-) patients as controls.

<>>

Target patient population (Insert a description of target population and indication studied)

20 HIV (+) patients with the following requirements:

Age 19 and older,

Hemoglobin >8g/dl , Absolute neutrophil count >750/mm³, Platelet count >75,000cells/mm³, AST < 5 times the upper limit of normal (ULN),

Bilirubin < 2.5 times ULN, Alkaline phosphate < 5 times ULN, Creatinine < 2.5 mg/ml

Non- smoker (quite smoking at least 6 months)

Controlled Type II diabetes

Controlled hypertension

Non bisphosphate user

Non- bruxer

Misch Available Bone classification divisions A, B, C

Misch Bone Density classification D1, D2, D3

Minimal available bone width 5mm

Minimal available bone height 10mm

Minimum bone graft with freeze dried demineralised bone upon implant placement

Extraction site has to be healed up for minimum 3 months for mandibular and 6 months for maxillary before implant placement

Flap or flapless implant placement with surgical stent as guidance

Implant supported restorations are limited to the following edentulous areas:

Mandibular arches, excluding 3rd molar areas

Maxillary anterior and premolar areas

Exclude extensive bone graft involvement and sinus lift

No immediate implant loading

Total numbers of implant restorations are limited to;

Maximum of 4 units of fixed prosthesis with minimum 2 implants support for maxillary and mandibular anterior region,
 3 units bridge with 2 implant supports,
 2 units bridge with 2 implant supports,
 Single implant support crown

Permanent implant restoration 3 months after implant placement for mandibular and 6 months for maxillary.

All implant supported restorations will be cement-retained restorations.

Dental material: either full metal restoration or porcelain fused with metal restoration.

20 HIV-negative patients following the same requirements as above.

Investigational product/comparator (*State the devices / products that will be investigated // used and for comparative studies also the comparator/s*)

1. Cone beam CT full facial scan on every patient before and after implant placement on surgical site single arch at 1 year, 2 year, 3 year follow up (i-CAT \$600 per patient x40 = \$ 24,000)
2. Facilitate Pro software convert Dicom images for implant placement design and surgical stent fabrication (\$12,000)
3. Surgical tools for implant placement:
 (syringe, needles, elevators, periotomes, extraction forceps #150 & #151, bone spreading chisels, bone grinder, bone trap, bone compactor, bone curette, osteotomes, resorbable and non-resorbable sutures, needle holders, scissors
 Surgical stent, two surgical bundles, two surgical trays, one surgical motor, two surgical handpiece heads, two full restorative trays and bundles, surgical saline bags for surgical irrigation, disposable irrigation kits for drill unit, disposable drills. Pulse oximetry) (\$ 30,000)
4. Root form implants of various sizes, cover screws (\$250 per implant x est. 80 = \$ 20,000)
5. Freeze dried demineralised bone as bone graft material (\$ 100/ 0.5cc vial x est.20 = \$ 2,000)
6. Resorbable membrane (\$ 100/ membrane x est. 20 = \$ 2,000)
7. Poly vinyl siloxane impression materials (\$ 4,000)
8. Prosthodontic instrument kits plus laboratory fee (impression transfer material, implant abutments, implant analogues, Cresco Precision system)
 (\$ 400 per implant restoration x est. 80 = \$32,000)
9. Two WhipMix Semi- adjustable articulators (\$ 800 x 2 = \$1,600)
10. Half-time patient coordinator (\$ 18,000 or neg.)
- *11. Computer for information storage and portable printer (\$ 3,000)
12. SLR camera with Macro-lens and flash (\$ 2,500)
13. Histological examination of 40 bone biopsies processed at UAB Anatomic Pathology Lab, including special stains and decalcification (\$ 8,000)
14. Processing of failed implants at the UAB Bone Core facility with subsequent histologic examination of implant-bone interface (\$200.00 per failed implant x est. 5 = \$1,000)
15. Journal publication expenses (\$2000.00)
16. Travel expenses to national and/or international meetings by the PI investigator and one co-investigator (\$ 4000.00)

Total budget: \$166,000

Outcome variables (Indicate which variable is the primary variable for the study)

Efficacy (*List all efficacy variables and indicate clearly your primary outcome variable*)

The primary variable examined will be the treatment outcome as measured according to the Albrektsson and Zarb criteria for implant success. Patients will be examined at each interval for the presence of pain, infection, mobility, and radiographic bone height of each implant

Additional clinical assessments (*Describe use of any additional clinical assessments e.g. clinical photographs etc.*)

1. All selected patients will have prior medical authorization to have surgical procedure performed. Patients will undergo complete oral clinical examination as well as cone beam CT scan, selected periapical and vertical bitewing radiographs on planning implant placement site, full mouth photography, diagnostic casts, and surgical stent before implant placement.
2. Cone Beam CT on the implant sites of arches at 1 year, 2 years and 3 years post placement follow-up (Cone Beam CT provides 1:1 ratio image, view in 3- dimensions, limited radiation exposure). The images will be evaluated by the dental radiologist.
Compare accuracy and efficiency of Cone Beam CT image of alveolar bone around implant in 3-dimensions vs. of conventional standard X-ray examination of bone lost around implant in 2-dimensions.
3. Histologic examination of the bone biopsy from the implant sites will provide scientific evidence of the bone changes that may occur in the process of implant osteointegration under immunocompromised conditions.
4. Photograph during implant restoration procedure and after complete restoration.
5. Patient post-implant restoration survey (such as: general satisfaction, social life, mastication on hard food, comfort).

Statistical methods (*Describe as relevant the statistical methods to be used, the populations to be analysed (e.g. intention to treat, per-protocol), and any interim analyses*)

Descriptive statistics will be applied to acquire the mean parameter values, range, and implant success rate as determined by the Albrektsson and Zarb criteria.

With rigorous inclusion/exclusion criteria proposed, parametric data will be analysed using ANOVA methods. Nonparametric (yes/no) criteria will be analyzed with the Chi-Square method.

Publications / Presentations (*Describe your plans with regard to publications or public presentations i.e. what journals or conferences/meetings*)

Peer reviewed journals such as: Journal of American Dental Association, Journal of Prosthodontics, Journal of General Dentistry.

Oral platform presentations at various national and international dental meetings at Astra's discretion

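### The creatinine eligibility limit is printed in mg/ml, which makes it 250 mg/dl; the unit is very probably a slip for mg/dl and should be confirmed and corrected.

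*Combined protocol and SAP*

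**What the plan says.** The protocol synopsis, under Target patient population, lists the laboratory requirements for the HIV-positive group, introduced by "20 HIV (+) patients with the following requirements". The renal requirement is "Creatinine < 2.5 mg/ml". It appears once, and the documents contain no other creatinine limit or renal criterion.

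Two other entries in the list help in reading it. Hemoglobin, the only other limit given as mass per volume, is per decilitre: "Hemoglobin >8g/dl". Bilirubin carries the same number as creatinine but relative to the upper limit of normal (ULN): "Bilirubin < 2.5 times ULN".

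The control group is bound by the same list: "20 HIV-negative patients following the same requirements as above". Under Additional clinical assessments the synopsis adds a general safeguard: "All selected patients will have prior medical authorization to have surgical procedure performed". That sentence sets no renal threshold.

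**The concern.** An upper limit in an eligibility list is there to keep some candidates out. A creatinine limit of 2.5 per millilitre is so high that, taken literally, it appears to keep out nobody. The list would then contain a renal criterion in name only, for patients about to have surgery.

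What is at stake is the safety screen and the description of who was eligible. If staff silently read the unit as mg/dl, the limit they applied differs from the published one by a factor of 100, and a reader cannot tell from the document which was used. Nothing in the sample size, the comparison between groups or the analysis turns on this.

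**Working it through.** **Inputs from the documents**

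- Creatinine limit as printed: below 2.5 mg/ml (Target patient population).
- Hemoglobin limit: above 8 g/dl (same list).
- Bilirubin limit: below 2.5 times ULN (same list).
- Patients covered: 20 HIV-positive and 20 HIV-negative, so 20 + 20 = 40.

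**Assumptions, not in the documents**

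- The criterion refers to blood creatinine.
- Candidates' values lie between 1 and 50 mg/dl.

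**Step 1: convert the printed limit.** With 1 dl = 100 ml,

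2.5 mg/ml × 100 ml/dl = 250 mg/dl.

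The ratio of the printed limit to the same number read in mg/dl is 250 / 2.5 = 100.

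**Step 2: see whom each reading excludes.**

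| Reading | Excludes | Within the assumed 1 to 50 mg/dl |
|---|---|---|
| As printed, mg/ml | 250 mg/dl and above | nobody |
| As mg/dl | 2.5 mg/dl and above | values from 2.5 to 50 mg/dl |

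The printed limit is 250 / 50 = 5 times the top of the assumed range. The result does not depend on the choice of 50: the printed limit excludes nobody for any top value below 250 mg/dl.

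**Step 3: find where the readings disagree.** They classify a candidate differently only when creatinine is at least 2.5 and below 250 mg/dl. The documents do not say how many of the 40 planned patients fall there.

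**Step 4: ask what was intended.** Two things point to mg/dl. Hemoglobin is stated per dl, and 2.5 falls inside the assumed range when read per dl but not when read per ml. A less likely alternative is that 2.5 times ULN was meant, given the bilirubin entry. That limit would equal 2.5 mg/dl only if the laboratory's ULN were exactly 1 mg/dl (2.5 × 1 = 2.5), and the documents give no ULN. So the intended limit has to be confirmed and cannot simply be assumed.

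**The case against.** The strongest case against is that this is a typing slip with no demonstrated consequence. The same list has other slips of wording, staff would probably read mg/dl without a second thought, and medical authorization is required before surgery. The primary outcome, implant success, does not depend on the unit. This stands as an argument about weight, and it is why the point is minor. It does not remove the point, because this slip changes a numeric decision limit and the authorization requirement names no renal threshold that could replace it.

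A second objection is that mg/dl is an inference, and a carry-over of the bilirubin limit is possible. That also stands. It is a reason to confirm the limit before amending it, not to leave the text alone.

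A third is timing. The planned study period ended in "December 2014" and the document is dated "August 30, 2019", so a correction probably cannot change enrolment. It can still correct the published criterion. A look back at patients' values is possible only if they were kept, and the documents describe no screening log or laboratory schedule.

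Lastly, the unit might have been misread when the PDF was converted to text. This cannot be ruled out from the text alone, but nothing suggests it: the hemoglobin unit in the same list came through as g/dl. A glance at the source page would settle it.

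**Conclusion.** The point holds: the limit is wrong as written. The 100-fold conversion rests on the document alone. That the printed limit excludes nobody rests on two stated assumptions: that blood creatinine is meant, and that no candidate reaches 250 mg/dl. That mg/dl was intended is very probable but not stated anywhere.

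The severity is minor. The error disables, on paper, the only renal threshold for both groups, but its practical effect is likely small and may be nil.

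**What to change.** First, have the principal investigator, with medical input, confirm the intended limit against the unit the laboratory reports. If it is mg/dl, as expected, change the criterion to creatinine below 2.5 mg/dl. If a multiple of ULN was meant, say so explicitly.

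If screening is complete, establish from the screening records which limit was applied, list any enrolled patient with creatinine of 2.5 mg/dl or more (or at or above the confirmed limit, if different), and state the corrected criterion when the trial is reported. If the values were not kept, say that.

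The cost is one unit in the text and, where records exist, a check of at most 40 patients' values. Sample size, procedures and analysis are unchanged.

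### Radiographic bone height is listed under the primary outcome, but nothing in the plan keeps HIV status from the person who reads the images, and the image type and film reader are not named.

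*Combined protocol and SAP*

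**What the plan says.** - **Primary outcome** (Outcome variables, Efficacy): "The primary variable examined will be the treatment outcome as measured according to the Albrektsson and Zarb criteria for implant success". The next sentence lists what is examined at each interval: "pain, infection, mobility, and radiographic bone height of each implant". No bone-loss threshold, unit or precision is given.
- **Images and reader** (Additional clinical assessments, item 2): the scans are "Cone Beam CT on the implant sites of arches at 1 year, 2 years and 3 years post placement follow-up", and "The images will be evaluated by the dental radiologist". The same item plans a comparison of CT with conventional 2-D films. It does not say who reads the films, or which of the two supplies bone height for the primary outcome.
- **Radiologist on the team** (Investigator, B. Co-Investigators, item 5): "Radiologist, Associate Professor, Director of Clinical Operations and Dental Radiology, UAB Diagnostic Science Department". No other radiologist is listed.
- **Groups** (Study design; Study centre(s)): HIV-positive patients are compared with HIV-negative controls, without randomisation. Twenty come from the 1917 Dental Clinic and twenty from the School of Dentistry's patients.
- **Analysis** (Statistical methods): ANOVA for measurements and chi-square for yes/no criteria. No significance level, SD or expected success rate is stated.
- **Masking**: no section mentions masking, coded or de-identified images, reading order, a second reader or an agreement check.

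**The concern.** Exposure here is a patient characteristic, so patients and treating clinicians cannot realistically be masked. Image reading is the component where masking is feasible, because a scan does not itself display HIV status. Yet the plan has no step that keeps HIV status or clinic of origin from the reader. The two groups come from different patient pools, so a name, chart number or referring clinic attached to an image could reveal the group.

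If the reader knows the group and reads even slightly differently because of it, the shift is added to the group contrast. ANOVA on bone height and chi-square on success both estimate the sum of the HIV effect and the reading shift, and neither can split them. The bias could run either way. Strict reading of HIV-positive images would create a difference, and lenient reading would hide one.

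**Working it through.** The plan states no figure on this point, so there is nothing to reproduce. The check is a reading of the text followed by an illustration.

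**Step 1. What the text establishes.**

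| Question | Answer in the documents |
|---|---|
| Is bone height part of the primary assessment? | Yes (Outcome variables, Efficacy) |
| Who reads the CT? | One role, the dental radiologist |
| Is that the co-investigator? | Inferred: the only radiologist listed |
| Who reads the 2-D films? | Not stated |
| Which image type gives primary bone height? | Not stated |
| Is the reader told HIV status or clinic? | Not stated |
| Is there any step to prevent it? | None described |

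**Step 2. Effect of a reading shift on the bone-height comparison.**

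Input from the protocol: n = 20 patients per group. Assumptions: two-sided 5% test, one value per patient, independent patients, no true difference, and a constant shift of d total between-patient SDs in one group. With two groups, ANOVA is the two-sample t test.

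- Degrees of freedom = 2 x 20 - 2 = 38; critical value = 2.024.
- Noncentrality = d x sqrt(n/2) = d x sqrt(10).
- False-positive rate = P(T > 2.024) + P(T < -2.024), where T is noncentral t with 38 degrees of freedom.

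| Shift d (SD) | Noncentrality | False-positive rate |
|---|---|---|
| 0 | 0 | 5.0% |
| 0.1 | 0.316 | 6.1% |
| 0.2 | 0.632 | 9.5% |
| 0.4 | 1.265 | 23.4% |
| 0.6 | 1.897 | 45.6% |

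The table is in SD units because the documents give no SD. Any translation to millimetres depends on an assumed one. A 0.2 mm shift is 0.4 SD if the SD is 0.5 mm (23.4%), but 0.2 SD if the SD is 1.0 mm (9.5%).

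**Step 3. Effect on the success classification.**

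These are exact rejection probabilities of the uncorrected chi-square test, with 20 independent patients per group and a two-sided 5% test. The success rates are assumed.

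- *Creating a difference.* True success is 95% in both groups. If 10% of true HIV-positive successes are read as failures, the observed rate becomes 0.95 x 0.90 = 85.5%, and rejection rises from 1.2% to 14.1%. With true success of 90%, the same misreading raises it from 3.9% to 12.2%.
- *Hiding a difference.* True success is 95% v 75%. Lenient reading that lifts the HIV-positive rate to 85% cuts power from 44% to 15%.

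**Step 4. Volume of images to code.** 40 patients x 3 follow-up visits = 120 CT scans, plus the 2-D films, whose number the plan does not give.

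**The case against.** The strongest reply is that the plan is a synopsis, and silence about masking does not mean that reading is unmasked. Several stronger conclusions are tempting, and the documents do not support them.

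- *That the reader knows HIV status.* Nothing says so. All 40 patients are treated in the same clinic and scanned at one site, so scan location does not reveal group. The listed radiologist belongs to a different department, and the director of the 1917 clinic is a different co-investigator. Knowledge is possible, not shown.
- *That one co-investigator reads every image.* The reader sentence closes the CT item only. It may not govern the reading that feeds the primary outcome.
- *That the damage is irreparable.* The scans are digital (Investigational product/comparator, item 2, refers to Dicom files). If they are kept, they can be coded and re-read by a masked reader. Analysis cannot repair a first unmasked reading, but a fresh reading could.
- *That the measurement is sub-millimetre, or that a given shift in millimetres has a known effect.* The documents give no threshold, precision or SD.
- *That only about five failures are expected on the primary criterion.* That figure is a budget line for processing failed implants (item 14), not a forecast of success.
- *That one misread case moves an arm by five percentage points.* This holds per patient (1/20). Bone height is recorded per implant, about 80 are budgeted, and at an assumed 40 per arm one implant is 2.5 points (1/40).

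These replies limit how firmly the problem can be stated and how large it can be said to be. They do not supply a safeguard: the plan still has none.

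**Conclusion.** The point holds as a gap in the design. Bone height sits under the primary outcome, the groups are non-randomised and come from different patient pools, and no step keeps group from the reader. The planned tests could not tell a group-dependent reading shift from an HIV effect. This goes beyond missing wording, because coding has to be arranged before the images are read if the first reading is to be protected.

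The size of any bias is unknown. The rates of about 6% to 46% are illustrations for shifts of 0.1 to 0.6 SD. They rest on an assumed 5% level, independent patients and a uniform shift in one group, and the documents show none of these shifts to be likely. The change should be made, chiefly because it is cheap. If images are already coded in practice, the sponsor need only say so.

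**What to change.** Add to Additional clinical assessments, item 2:

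> Follow-up cone beam CT and radiographic images are exported under a study code with name, chart number and clinic of origin removed, and are read in random patient order within each visit batch. The radiologist has no access to HIV status, and records and locks bone height for that batch before any linkage to group. The existing coordinator holds the key.

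State also which image type supplies bone height for the primary outcome, and who reads the films.

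Visit year should stay on the images, and they should not be shuffled across years. Doing either would mean holding early scans until later visits are complete. That would conflict with examination at each interval and with the December 2011 date for first data.

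Cost: some coordinator time to code about 120 CT scans plus the films. The budget already carries a "Half-time patient coordinator" (Investigational product/comparator, item 10). No second reader, extra visit or larger sample is needed.

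Limit: pain, infection and mobility remain assessed without masking, so the primary outcome is only partly protected. The report should say so.

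### The promised accuracy comparison of cone beam CT with conventional X-ray has no reference standard, so the design can estimate only agreement between the two

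*Combined protocol and SAP*

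**What the plan says.** **The comparison.** Additional clinical assessments, item 2, contains the task "Compare accuracy and efficiency of Cone Beam CT image of alveolar bone around implant in 3-dimensions vs. of conventional standard X-ray examination". The conventional side of it is "conventional standard X-ray examination of bone lost around implant in 2-dimensions". The dental radiologist reads the images. Neither accuracy nor efficiency is defined. The same item supports the use of cone beam CT with the remark "Cone Beam CT provides 1:1 ratio image, view in 3- dimensions, limited radiation exposure".

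**Timing of the images.** Item 2 schedules "Cone Beam CT on the implant sites of arches at 1 year, 2 years and 3 years post placement follow-up". Item 1 lists "selected periapical and vertical bitewing radiographs on planning implant placement site", in a sentence about the work-up before placement. Objective 2 names cone beam CT and vertical bitewings for examining osseous integration, without dates. The primary variable (Outcome variables, Efficacy) calls for radiographic bone height of each implant at every examination interval, but names no modality and dates no interval.

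**Tissue.** Objective 3 plans biopsies at placement and from failing sites. Item 14 under Investigational product/comparator budgets for "Processing of failed implants at the UAB Bone Core facility with subsequent histologic examination of implant-bone interface", costed "per failed implant x est. 5". Item 4 of the same list costs implants "per implant x est. 80".

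**Analysis.** Statistical methods lists descriptive statistics, ANOVA methods, and chi-square for yes/no criteria. None is tied to the imaging comparison.

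**The concern.** A claim that one imaging method is more accurate than another needs a third value to judge both against. If the CT and the film give different bone heights for the same implant, nothing in the plan says which is wrong. An accuracy statement drawn from these data would have no declared basis, and the plan intends journal publication.

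Two further gaps bear on the same sentence. No analysis is assigned to the comparison, and the listed methods are given without any pairing or clustering structure. The conventional films that would make up half of each pair also have no date after placement.

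**Working it through.** The plan gives no figure for this comparison, so there is nothing to reproduce. The check has four steps.

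**1. Could anything in the plan serve as the reference?**
- *Placement biopsies (Objective 3).* They are taken when the implant goes in, before any bone around it can be lost. They cannot give the true bone level at a follow-up image.
- *Interface histology (budget items 14 and 4).* Estimated failures over estimated implants: 5/80 = 6.25%. The other 75/80 = 93.75% have no such tissue. The 5 are all failures, and no text links them to an image.
- *Cone beam CT itself.* The 1:1 remark gives a reason for using CT and does not declare it the truth. If CT were the reference, its own accuracy could not be tested.

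None of the three fills the gap.

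**2. How many image pairs have a stated date with an implant in place?**

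| Time | Cone beam CT | Conventional film |
|---|---|---|
| Before placement (no implant) | dated | dated |
| Year 1 | dated | no date |
| Year 2 | dated | no date |
| Year 3 | dated | no date |

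The count is 0 of 3 follow-up visits. This counts explicit dates and does not predict how many pairs will exist: Objective 2, the reference to bone lost around the implant, and bone height at every interval all imply follow-up films.

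**3. Would a test of mean difference answer the question?** The limits of agreement are mean difference ± 1.96 × SD of the paired differences. Take a mean difference of 0 and an assumed SD of 0.5 mm. The limits are ±1.96 × 0.5 = ±0.98 mm. A test of means would find no difference, yet single implants could differ by almost 1 mm in either direction.

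**4. How precise would an agreement analysis be?** Inputs: 40 patients (Study centre section) and 80 implants (budget estimate), with one image pair per implant. The 95% confidence half-width of each limit is

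1.96 × SD × √(1/n + 1.96²/(2(n − 1))).

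- n = 80 (implants within a patient uncorrelated): √(0.0125 + 0.0243) = 0.192, and the half-width is 0.376 SD.
- n = 40 (implants within a patient fully correlated): √(0.0250 + 0.0493) = 0.272, and the half-width is 0.534 SD.
- A simulation of 40 patients with 2 implants each (an assumed even split), with the SD taken from variance components, gave ±0.38, ±0.43 and ±0.53 SD at within-patient correlations of 0, 0.5 and 1.

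The documents give no SD. At assumed SDs of 0.2, 0.5 and 1.0 mm, the half-widths would be 0.08 to 0.11, 0.19 to 0.27 and 0.38 to 0.53 mm. These figures describe the proposed analysis. They do not measure an error in the plan.

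**The case against.** The strongest reply is that this is one sentence about an additional assessment in a short synopsis, with no test or claim threshold attached, and that accuracy may be loose wording for comparison. That limits the severity. It does not supply a reference, and if the word is loose, replacing it costs nothing.

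A reader might infer that no follow-up films are planned and the comparison is impossible. The documents do not support this. Objective 2 and the primary variable's bone height at every interval make films at the CT visits a natural reading. The films are undated, which is not the same as unplanned. The primary-variable sentence does not name a modality, so the gap in timing remains.

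A reader might also infer that ANOVA cannot handle paired images or several implants per patient. That goes too far. ANOVA methods include repeated-measures and random-effects models, which can do both. What stands is narrower: the plan assigns no method to this comparison and states no pairing or clustering structure, and a test of mean difference would still not quantify agreement on individual implants.

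**Conclusion.** The point holds and is minor. As designed, the study can estimate how far cone beam CT and conventional X-ray agree, but not how accurate either is. The only follow-up tissue tied to implants is expected for about 5 of 80 (6%), all failures. The 80 and the 5 are the plan's own budget estimates, and fewer paired implants would widen the intervals above.

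The two parts differ in reach. The missing reference affects only this additional assessment. The undated films also touch the bitewing part of Objective 2, and possibly the radiographic bone-height element of the primary outcome. It would be wrong to conclude from this that the comparison of HIV-positive with HIV-negative patients is invalid: that comparison does not rest on showing one modality more accurate than the other.

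**What to change.** 1. In Additional clinical assessments item 2, replace accuracy with agreement between modalities.
2. In Statistical methods, add one analysis: for implants with both images at the same visit, report the mean difference in bone height and the 95% limits of agreement with confidence intervals, allowing for implants and repeat visits clustered within patients.
3. Define efficiency, or delete the word.
4. Reconcile Objective 2, the primary-variable sentence and items 1 and 2 on when conventional films are taken.
5. If follow-up films were not intended, delete the comparison and reword Objective 2 to match, without adding imaging.

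A kappa statistic is not proposed, because the plan defines no yes/no radiographic reading.

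**Cost.** If films were intended, the cost is wording and one small paired analysis on images already intended. If not, it is one deletion and a matching edit to Objective 2. Neither route adds patients or imaging. The downside is a weaker claim, limited to measurements that both modalities provide, with precision in mm unknown until an SD is available.
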